9.4.2 Missing covariate data

We expect very low missing covariate data as used in primary efficacy analyses. Missing rates of 5% and lower were discussed to have no consequences on the estimates. (5) Therefore, missing data will be handled with full information maximum likelihood estimation. In case of a missing data rate of above 5%, we will repeat the primary efficacy analysis after multiple imputation as sensitivity analysis.

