Logistic regression models for the binary endpoints described above will be performed. Physician related variables (age, sex, medical experience, emergency experience, medical specialist) and patient related variables (chief complaint, triage level, charlson-comorbidity index and length of ED stay) as well as site will be added as independent predictors. Predictor estimates will be and presented as Odds Ratios alongside 95% confidence intervals using Forest plots. Models will be repeated without physician related variables to explore the potential influence of missing values in physician related covariates.

d) *Number of cases where a generated DDx list entails the primary diagnosis after 14d*

ICD-10 Codes provided form the CDDS will be automatically compared with the ICD-10 Code of the primary diagnosis at follow-up using a batch tool.(8) Contingency tables for patients with and without change in diagnosis (diagnostic discrepancy) will be reported.

14 Reporting Conventions

P-values ≥ 0.001 will be reported to 3 decimal places; p-values less than 0.001 will be reported as " <0.001 ". Other statistics will be reported as integers or rounded to one or two decimal places as appropriate.

15 Quality Assurance of Statistical Programming

A second statistician will review and independently reproduce the primary analyses and summary statistics. The reviewing statistician will have an overview of the entire analyses and will explicitly check the code producing tables as well as any other pieces of code as desired.

16 Summary of Changes to the Protocol and/or SAP

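### SAP 13 c): refitting without the physician variables changes the covariates and, by implication, the sample, so it cannot isolate the influence of missing physician data

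*SAP*

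**What the plan says.** SAP section 13 c) plans descriptive counts and then regression: "Logistic regression models for the binary endpoints described above will be performed". The predictors are of two kinds, plus site:

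- "Physician related variables (age, sex, medical experience, emergency experience, medical specialist", that is, five physician variables;
- "patient related variables (chief complaint, triage level, charlson-comorbidity index and length of ED stay) as well as site will be added as independent predictors".

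Estimates for the predictors are to be "presented as Odds Ratios alongside 95% confidence intervals using Forest plots". The physician odds ratios are therefore among the results to be shown.

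The only provision for missing physician data in these models is the repeat: "Models will be repeated without physician related variables to explore the potential influence of missing values in physician related covariates".

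The general rule in section 9.4.2 is worded for another analysis. It opens with "We expect very low missing covariate data as used in primary efficacy analyses" and continues "In case of a missing data rate of above 5%, we will repeat the primary efficacy analysis after multiple imputation as sensitivity analysis". Section 16.1 repeats this for the primary analyses. The covariates of the primary model in section 11.1 are chief complaint, age, sex and the Charlson index. None of the five physician variables is among them, so these rules do not cover section 13 c).

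**The concern.** The section names a purpose, to explore "the potential influence of missing values in physician related covariates", and a procedure that does not isolate it. The first model adjusts for the physician variables and, under default fitting, uses only patients whose physician has complete data. The repeat removes the five variables, and the excluded patients return. An odds ratio can then move for two unrelated reasons:

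1. Predictors were removed. The estimate changes through confounding (physician mix differing between sites or patient groups) or through non-collapsibility of the odds ratio, even if no value is missing.
2. The patients changed. This is the only part that concerns missing data.

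The two effects can add up, or they can cancel. A reader of the two forest plots could doubt sound results or be reassured about biased ones. For the physician predictors there is nothing to compare, because the repeat leaves them out.

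**Working it through.** The SAP states no figure here, so there is none to reproduce. The question is whether the planned comparison can separate the two effects, and large-sample simulation answers it.

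**Inputs from the SAP (13 c).** Logistic regression; five physician variables removed in the repeat; patient variables and site kept; odds ratios reported.

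**Assumptions.** Missing rates, effect sizes and missingness mechanisms are all assumed, because the SAP gives none. Complete-case fitting of the first model is inferred from the stated purpose.

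**Set-up.** n = 500,000 per scenario; x is a binary patient or site predictor with prevalence 0.5; z is a physician variable with SD 1 and mean shift s when x = 1.

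logit P(y = 1) = -0.5 + b_x·x + b_z·z

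Four fits give the odds ratio for x:

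- F-all: full model, nothing missing (the reference)
- F-cc: full model, complete cases (the plan's first model)
- R-cc: model without z, same complete cases (not planned)
- R-all: model without z, all patients (the plan's repeat)

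The plan compares F-cc with R-all. F-cc to R-cc is the covariate change alone, and R-cc to R-all is the sample change alone.

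| Scenario | s, b_x, b_z | Missing | F-all | F-cc | R-cc | R-all |
|---|---|---|---|---|---|---|
| A: completely at random, z related to x | 0.8, 0.4, 0.7 | 30% | 1.49 | 1.48 | 2.36 | 2.37 |
| B: completely at random, z independent of x | 0, ln 2, 1.0 | 30% | 2.01 | 2.01 | 1.78 | 1.78 |
| C: completely at random, z unrelated to y | 0.8, 0.4, 0 | 30% | 1.49 | 1.50 | 1.49 | 1.48 |
| D: missingness depends on x and y | 0.8, 0.4, 0.7 | 21% | 1.50 | 2.30 | 3.66 | 2.38 |
| E: missingness depends on z and y | 0, 0.4, 0.3 | 23% | 1.48 | 1.48 | 1.45 | 1.47 |

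In D the missing probability is 0.45 when x = 1 and y = 0, and 0.15 otherwise. In E it is 0.6 when z > 0 and y = 0, and 0.1 otherwise.

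**Reading.**

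- *False signal.* In A the planned comparison moves by 2.37 / 1.48 = 1.60 although missingness has no influence; confounding by z accounts for it. In B it moves from 2.01 to 1.78 through non-collapsibility alone. In both, R-cc and R-all agree.
- *Control.* In C the physician variable does not predict the rating, and the planned comparison is clean (1.50 v 1.48).
- *Hidden bias.* In D the complete-case estimate is off by 2.30 / 1.50 = 1.53, yet the planned comparison shows only 2.38 / 2.30 = 1.03. R-cc against R-all shows 3.66 v 2.38.
- *Physician odds ratio.* In E the odds ratio for z goes from 1.35 to 1.89 in the complete cases. The odds ratio for x hardly moves, and the repeat contains no z.

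**What the extra reduced fit cannot show.** Take a true site odds ratio of 1.0, sites 0.5 SD apart in experience, about 29% missing, and missingness depending only on site and experience. For experience log odds ratios of 0.4, 0.7 and 1.0 per SD, F-cc is unbiased (1.00, 1.01, 0.99). R-cc and R-all nevertheless differ: 0.94 v 1.22, 0.91 v 1.38, 0.85 v 1.49. A separate simulation with missingness again depending on site and experience gave 1.00 v 1.22, 0.99 v 1.38 and 0.97 v 1.51. A gap between the two reduced fits therefore shows that the complete-data patients differ. It does not show that the full model is biased.

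**The case against.** Four points can be made for the plan.

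*The repeat is descriptive.* The section only explores; it sets no threshold and no rule for discarding a model. This stands. A reader might infer that the SAP uses the comparison to decide whether the usefulness and impact models can be trusted, but the document gives it no such role.

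*Complete-case fitting is not stated.* This also stands, and the point must be labelled an inference. It does not rescue the check: if the sample did not change, the repeat would only remove covariates and would carry no information about missing values.

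*The sizes are invented.* True. They depend on chosen effects and missingness mechanisms, and scenario C shows no distortion when physician variables do not predict the rating. The section does enter them as predictors of the rating, so it treats an association as plausible.

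*The obvious repair overclaims.* A reader might infer that fitting the reduced model on both samples would by itself reveal bias from missing physician data. The last simulation shows otherwise: the reduced fits can differ while the full complete-case model is sound. Neither reduced fit contains the physician odds ratios. This objection stands and shapes the fix.

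**Conclusion.** The point holds as a minor one. The planned comparison mixes a covariate change with an implied sample change, so neither a shift nor its absence in the patient and site odds ratios can be attributed to missing physician data. It offers no check at all on the physician odds ratios.

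The conclusion rests on the inferred complete-case fitting. A false signal also requires physician variables that predict the ratings. How large the distortion would be in this trial cannot be derived from the SAP; the simulated values show only that errors in both directions are possible.

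The analysis is exploratory and sits under other analyses. The primary endpoint, the treatment effect, the safety analyses and the sample size are unaffected.

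**What to change.** In section 13 c):

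1. State that the full model is fitted on patients with complete physician data, if that is intended, and report how many patients and physicians are excluded.
2. Fit the model without physician variables twice: on the complete-data patients and on all patients.
3. Read full against reduced within the complete-data patients as the effect of adjustment. Read the two reduced fits against each other only as evidence on whether the complete-data patients differ, not as proof of bias in the full model.
4. To check the full model, including the physician odds ratios, refit it after multiple imputation of the physician variables, with the outcome in the imputation model, and compare it with the complete-case fit.

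The cost is a few extra fits per statement and a few sentences; no new data are needed. The imputation step relies on data missing at random, so it would suit a mechanism like D but could not be counted on under one like E, where missingness depends on the unobserved physician value itself. The report should say so. Section 9.1 provides for final SAP changes after data review and before any efficacy analysis, which is a natural time for this edit.

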18.1 Figure 1 – Flow diagram

[figure not shown]

Figure 1 Trial profile

* Drop out if patient left ED before clinical examination or if no physician was allocated to the enrolled patient at the end of the study nurse's shift)

18.2 Table 1 – Baseline Characteristics of the intention-to-treat population

	Intervention Group (n=XXX)	Control Group (n=XXX)
Site		
University Hospital Bern	XXX (XX%)	XXX (XX%)
Buergerspital Solothurn	XXX (XX%)	XXX (XX%)
Spital Tiefenau	XXX (XX%)	XXX (XX%)
Spital Muensingen	XXX (XX%)	XXX (XX%)
Phase		
1	XXX (XX%)	XXX (XX%)
2	XXX (XX%)	XXX (XX%)
3	XXX (XX%)	XXX (XX%)
4	XXX (XX%)	XXX (XX%)
5	XXX (XX%)	XXX (XX%)
6	XXX (XX%)	XXX (XX%)
Age (years)	XX (XX-XX)	XX (XX-XX)
Sex		
Male	XXX (XX%)	XXX (XX%)
Female	XXX (XX%)	XXX (XX%)
Chief complaint		
Fever	XXX (XX%)	XXX (XX%)
Abdominal pain	XXX (XX%)	XXX (XX%)
Syncope	XXX (XX%)	XXX (XX%)
Non-specific complaint	XXX (XX%)	XXX (XX%)
Triage level		
2	XXX (XX%)	XXX (XX%)
3	XXX (XX%)	XXX (XX%)
4	XXX (XX%)	XXX (XX%)
5	XXX (XX%)	XXX (XX%)
Referral type		
Self-referral	XXX (XX%)	XXX (XX%)
General practitioner	XXX (XX%)	XXX (XX%)
Hospital	XXX (XX%)	XXX (XX%)
Air rescue	XXX (XX%)	XXX (XX%)
Ambulance	XXX (XX%)	XXX (XX%)
Unknown	XXX (XX%)	XXX (XX%)
Admission type		
Self-admittance	XXX (XX%)	XXX (XX%)
Ambulance	XXX (XX%)	XXX (XX%)
Air Rescue	XXX (XX%)	XXX (XX%)
Unknown	XXX (XX%)	XXX (XX%)
Charlson Comorbidity Index		
0	XXX (XX%)	XXX (XX%)
1-2	XXX (XX%)	XXX (XX%)
3-4	XXX (XX%)	XXX (XX%)
≥5	XXX (XX%)	XXX (XX%)
Unknown	XXX (XX%)	XXX (XX%)
Data are median (IQR) or n (%).		

18.3 Table 2 – Primary and secondary efficacy outcomes

	Intervention Group		Control Group		Measure of effect	Adjusted effect (95% CI)	p value
	N	n (%) or median (IQR)	N	n (%) or median (IQR)			
Primary outcome							
Diagnostic quality risk	XXX	XX (XX%)	XXX	XX (XX%)	OR	X-XX (X-XX to X-XX)	<X-XXX
Secondary outcomes							
Death	XXX	XX (XX%)	XXX	XX (XX%)			
Unscheduled medical care	XXX	XX (XX%)	XXX	XX (XX%)	OR	X-XX (X-XX to X-XX)	<X-XXX
Unscheduled medical care within 7 days	XXX	XX (XX%)	XXX	XX (XX%)	OR	X-XX (X-XX to X-XX)	<X-XXX
Unscheduled medical care within 3 days	XXX	XX (XX%)	XXX	XX (XX%)	OR	X-XX (X-XX to X-XX)	<X-XXX
Unexpected ICU admission or upscale in care	XXX	XX (XX%)	XXX	XX (XX%)	OR	X-XX (X-XX to X-XX)	<X-XXX
Diagnostic discrepancy	XXX	XX (XX%)	XXX	XX (XX%)	OR	X-XX (X-XX to X-XX)	<X-XXX
ED costs in CHF	XXX	XX (XX to XX)	XXX	XX (XX to XX)	GMR	XX (XX to XX)	<X-XXX
Total hospital costs in CHF	XXX	XX (XX to XX)	XXX	XX (XX to XX)	GMR	XX (XX to XX)	<X-XXX
Safety Outcomes							
Serious adverse event (overall)	XXX	XX (XX%)	XXX	XX (XX%)			
Death							
Life-threatening illness or injury	XXX	XX (XX%)	XXX	XX (XX%)			
Permanent disability / incapacity	XXX	XX (XX%)	XXX	XX (XX%)			
Medical or surgical intervention to prevent life-threatening illness	XXX	XX (XX%)	XXX	XX (XX%)			
Injury or permanent impairment	XXX	XX (XX%)	XXX	XX (XX%)			
Congenital anomaly / birth defect	XXX	XX (XX%)	XXX	XX (XX%)			
Chronic disease	XXX	XX (XX%)	XXX	XX (XX%)			
Hospitalization or prolongation of existing hospitalization	XXX	XX (XX%)	XXX	XX (XX%)			

OR, Odds Ratio; GMR, Geometric Mean Ratio; ICU, intensive care unit; ED, Emergency department, CHF, Swiss Francs

18.4 Table 3 - Full-case review for diagnostic errors in a random subset. Items of the Safer Dx instrument compared between patients not randomly

		50 random patients with diagnostic quality risk	50 random patients without diagnostic quality risk	p value
Item 1	The documented history was suggestive of an alternate diagnosis, which was not considered in the diagnostic process.	XX (XX to XX)	XX (XX to XX)	<X-XXX
Item 2	The documented physical exam was suggestive of an alternate diagnosis, which was not considered in the diagnostic process.*	XX (XX to XX)	XX (XX to XX)	<X-XXX
Item 3	Data gathering through history, physical exam, and review of prior documentation (including prior laboratory, radiology, pathology or other results) was incomplete, given the patient's medical history and clinical presentation.	XX (XX to XX)	XX (XX to XX)	<X-XXX
Item 4	Alarm symptoms or "Red Flags" (i.e. features in the clinical presentation that are considered to predict serious disease) were not acted upon.	XX (XX to XX)	XX (XX to XX)	<X-XXX
Item 5	The diagnostic process was affected by incomplete or incorrect clinical information given to the care team by the patient or their primary caregiver.	XX (XX to XX)	XX (XX to XX)	<X-XXX
Item 6	The clinical information (i.e. history, physical exam or diagnostic data) should have prompted additional diagnostic evaluation through tests or consults.	XX (XX to XX)	XX (XX to XX)	<X-XXX
Item 7	The diagnostic reasoning was not appropriate, given the patient's medical history and clinical presentation.	XX (XX to XX)	XX (XX to XX)	<X-XXX
Item 8	Diagnostic data (laboratory, radiology, pathology or other results) available or documented were misinterpreted in relation to the subsequent final diagnosis.	XX (XX to XX)	XX (XX to XX)	<X-XXX
Item 9	There was missed follow-up of available or documented diagnostic data (laboratory, radiology, pathology or other results) in relation to the subsequent final diagnosis.	XX (XX to XX)	XX (XX to XX)	<X-XXX
Item 10	The differential diagnosis was not documented OR The documented differential diagnosis did not include the subsequent final diagnosis.	XX (XX to XX)	XX (XX to XX)	<X-XXX
Item 11	The final diagnosis was not an evolution of the care team's initial presumed diagnosis (or working diagnosis).	XX (XX to XX)	XX (XX to XX)	<X-XXX
Item 12	The clinical presentation at the initial or subsequent presentation was mostly typical of the final diagnosis.	XX (XX to XX)	XX (XX to XX)	<X-XXX
Item 13	In conclusion, based on all the above questions, the episode of care under review has a missed opportunity to make a correct and timely diagnosis.	XX (XX to XX)	XX (XX to XX)	<X-XXX
Items were rated from 1 (strongly disagree) to 7 (strongly agree) from two independent raters (kappa = x.x) p value are for group comparison using unpaired two-samples Wilcoxon tests				

18.5 Figure 2 – Interaction Plots (example)
Exploratory analyses may be presented using interaction plots.
